Our strategy for eEVAR is the novel intervention. This involves urgent CT angiography to confirm the diagnosis and plan endovascular repair whenever feasible: endovascular supracoeliac aortic balloon occlusion will be used to support less stable patients. Guidelines for anatomical restrictions to endovascular repair are given in Appendix II. Patients will then be transferred to the intervention suite or operating theatre. For those in whom aortic anatomy precludes endovascular repair, open repair will be performed. A minority of patients (~5%) will not have an AAA identified on CT scan, although another diagnosis may be indicated: these patients will be directed to appropriate care. Most of the endovascular interventions will involve an aorto-uni-iliac graft with subsequent femoro-femoral cross-over graft, with contralateral iliac occlusion. Interventional control of the aorta can be achieved using local/regional anaesthesia, with general anaesthesia being used later in the procedure as necessary. A few patients will not require a critical care bed post-operatively. The core laboratory will assess the technical success of the procedure from the post-operative CT scan, 3 months after intervention.

The control intervention is the standard current practice of open repair, with most patients, including all the less haemodynamically stable patients, being taken directly to the operating theatre for laparotomy and open repair without confirmation of ruptured AAA by diagnostic imaging (although AAA may have been confirmed by ultrasonography). Aneurysms will be repaired by cross-clamping the proximal aorta and then inserting a prosthetic inlay graft. The very stable patients may undergo diagnostic imaging before laparotomy. At laparotomy a minority of patients will not have ruptured aneurysm, some may have AAA without rupture and some may have no aneurysm. All laparotomies will be conducted under general anaesthesia and patients will require a critical care bed post-operatively. There will be no requirement for post-operative CT scan unless this is indicated clinically.

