Both experimental (endovascular) and control (open surgery) interventions will follow an integrated care pathway from ambulance through Accident & Emergency, based on the JRCALC 2006 guidelines for abdominal trauma [19], see Appendix II. These guidelines limit fluid resuscitation in conscious patients with a palpable radial pulse with permissive hypotension (70-80 mm Hg). Physiological viability will be calculated for all patients using the Hardman index [20]. Guidelines will be provided for anaesthetic and critical care (Appendix II). Post-operatively statins will be recommended for all patients.

Frequency and duration of follow-up

All patients with ruptured AAA will be reviewed as an outpatient at 3 months (if they have been discharged) and again at 1 year after aortic repair. EQ-5D questionnaires for quality of life will be administered at 3 months, 1 year and again mid-term (between 2.5 and 4 years) after AAA repair. Patients with endovascular repair will require one post-operative CT scan (at 3 months after repair) and then the local follow-up for patients with endografts, usually requiring either CT or duplex scan at 6 months and 1 year. During the first year information also will be collected on complications and interventions relating to ruptured aneurysm repair as well as major morbidities (e.g. myocardial infarction, stroke, renal failure & dialysis) or hospitalizations from other causes. All randomised patients, with or without rAAA will be flagged with NHS Information Centre for cause and date of death, based on the pre-operative consent (conditional NIGB approval shown in Appendix IV).

Arrangements for randomization

Randomisation will be available at all times (24/7) by either telephone or internet using the services of thesealedenvelope.com: randomisation will be stratified by site and gender. For every patient randomized to normal care (open repair), 1 patient will be randomized to a strategy of endovascular repair. Randomisation will use a variable block size. This is a surgical trial of conventional versus a strategy of minimally invasive surgery, so patients & carers cannot be blinded to treatment allocation.

Inclusion and exclusion criteria

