Patient compliance is not an issue in a trial of emergency intervention. Patients will be flagged with the Health and Social Care Information Centre (previously NHS Information Centre) to ensure that post-discharge mortality data can be obtained: this includes patients who are subsequently identified as not having a ruptured AAA. After discharge, the trial will only actively follow-up patients with a confirmed diagnosis of rAAA for hospital and health economic data. It is anticipated that a minority of these (10%) will not attend for 1 year follow up, based on observations from the EVAR trials [15,16]. The ED-5Q questionnaire can be mailed to such patients not attending for 3m or 1 year follow ups. One later EQ-5D questionnaire at between 2.5 and 4 years after randomization will support mid-term cost-effectiveness evaluation: questionnaires will be mailed to surviving patients on a quarterly basis, immediately after the regular update of death reporting for the trial from Data Linkage and Extract Service.

Cost measurement

Microcosting methods will be used to record the costs associated with either intervention. Detailed information will be collected on the surgery undertaken for both patient groups including the stents used, time in theatre, use of blood products, contrast agents and endografts. All post operative interventions will be recorded, together with the days in hospital (critical care, general medical wards). These resource use data will be combined with appropriate unit costs. Previously collected detailed unit costs will be available (EVAR 1 and 2 trials), which will be updated during site visits to individual trust finance departments, and supplemented by unit costs from the NHS *Payment by results* databases. The impact of the surgical method on subsequent morbidity costs will be assessed. Each day in critical care will be assigned to a health care resource group (HRG) using mandated data collected for the critical care minimum dataset (CCMDS). These activity data will be combined with unit cost per hospital bed-day (by HRG) from the NHS *Payment by results* database. Readmissions will be recorded. The use of personal health services will be recorded by adapting previously developed questionnaires [27], and administering them at one year post randomisation. Community service use will then be valued using unit costs taken from published sources [28].

Number of centres involved – 30 includes Royal Free

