30 large centres have agreed to participate, but there are another 24 centres participating in the EVAR trials, some of whom are interested in participating e.g. Truro. All participating centres will have to satisfy key entry criteria for the trial, which will include emergency access to CT scan, willingness and ability to perform EVAR 24/7 and audited results for EVAR. All the centres listed have some experience of eEVAR for ruptured aneurysm. Early results from Cambridge and the Royal London hospital, albeit reporting a selected series of patients, indicate that their mortality for eEVAR is ≤15%.

Trial management, coordination, data checks and audits

The trial will be conducted according to the MRC Guidelines on Good Clinical Practice in Clinical trials, with a formal linkage to the International Circulatory Health group of Imperial College, which has provisional registration with UKCRC, to ensure staff support and training and careful monitoring of trial data. A Trial Steering Committee and a separate Data Monitoring and Ethical Committee will be established before the trial commences. The trial management committee (applicants and trial manager) will be responsible for recruitment and the proper running of the trial. Each centre will be checked for eligibility (at least 3 previous eEVAR procedures, appropriate organization) and receive a training visit. Each participating centre will nominate a local trial co-ordinator who will be responsible for reporting the data on all patients with ruptured aneurysm at that centre on a web-based case record system. The trial manager periodically will visit the trial centres to provide refresher training on taking consent, monitor patient consent and data quality.

Pilot feasibility study

This has been conducted in Nottingham and the results published [10]. First this trial showed clearly that a diagnostic CT scan neither resulted in increased mortality nor delayed the time to definitive procedure. Second, the Nottingham study demonstrated the feasibility of a randomised trial, with randomisation prior to CT scan, but was under-powered, underscoring the need for a multi-centre trial design. Third, an effective strategy for patient consent was developed. In that study, the authors addressed a number of the issues which will be relevant to the

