Patients have provided consent for review of their routine clinical data for up to 5 years and for quality of life assessments at 3 and 12 months following randomization. They have not formally given signed consent for a mid-term quality of life assessment but the Chairman of the lead Research Ethics Committee for the trial has proposed that return of the mid-term quality of life assessment would imply consent.

Trial documentation

This will be kept securely at Imperial College (duplicate database at the University of Cambridge) for at least 15 years after completion of the trial.

Planned analyses

The analyses will be carried out according to a detailed plan drawn up before the outcome data are inspected. A CONSORT diagram will describe the patient flow and exclusions. The groups will be considered as randomised (intention to treat) as a test of the interventional policy. The primary outcome is 30-day mortality, with secondary outcomes of 24-hour, in-hospital and 1-year mortality; each will be compared with a chi squared test, and the

estimated difference in proportions accompanied by a confidence interval. Adjustment for the baseline Hardman index will be undertaken in secondary analyses using logistic regression. Time to complications, re-interventions, and major morbidities after repair of ruptured aneurysm will be compared using the log-rank test and Cox regression.

Cost-effectiveness analysis will report the mean (95% CI) incremental costs and QALYs of eEVAR versus open repair at one year, and the probability that eEVAR is cost-effective compared to open repair, at different levels of willingness to pay for a QALY gained. The analysis will address issues posed by missing EQ-5D or cost data [32] and censoring [33]. Survival analysis will be used to extrapolate any within-trial differences in costs and QALYs to project lifetime cost-effectiveness [34,35]. Sensitivity analysis will test whether the results are robust to methodological assumptions. The effect of the algorithm of care on the outcome of open surgery will be reviewed against national statistics. The statistical analysis plans will be published on the trial website before any analysis commences.

Subgroup analyses

A limited number of predefined subgroups will be compared using tests of interaction, only for the primary outcome (in-hospital mortality), using logistic regression. Subgroups will be defined by age (continuous), gender, and Hardman index (continuous).

Frequency of analyses

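### Post-discharge quality-of-life, resource-use and morbidity follow-up is limited to confirmed ruptured AAA, so these comparisons cannot be made on all randomised patients as the protocol promises

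*Protocol*

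**What the plan says.** Patients enter the trial on a clinical suspicion of rupture (Inclusion and exclusion criteria). Proposed sample size takes 5% of each group to have no ruptured AAA, a fact that emerges only after randomisation.

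The analysis principle, under Planned analyses, is: "The groups will be considered as randomised (intention to treat) as a test of the interventional policy". The same section plans the economic comparison: "Cost-effectiveness analysis will report the mean (95% CI) incremental costs and QALYs of eEVAR versus open repair at one year". It gives no rule for patients who turn out not to have a rupture.

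Follow-up differs by type of data:

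- **Mortality** (Frequency and duration of follow-up): "All randomised patients, with or without rAAA will be flagged with NHS Information Centre for cause and date of death".
- **Outpatient review** (same section): "All patients with ruptured AAA will be reviewed as an outpatient at 3 months (if they have been discharged) and again at 1 year", with the visits counted from aortic repair.
- **Hospital and health-economic data** (Patient compliance and loss to follow-up): "After discharge, the trial will only actively follow-up patients with a confirmed diagnosis of rAAA for hospital and health economic data".

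Planned interventions describes how rupture is confirmed. In the endovascular-strategy arm it is by urgent CT angiography. In the control arm most patients go to theatre without confirmatory imaging, and "At laparotomy a minority of patients will not have ruptured aneurysm, some may have AAA without rupture and some may have no aneurysm".

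**The concern.** The protocol tracks deaths in everyone randomised but follows quality of life, resource use and morbidity after discharge only in a subset defined after randomisation. The test that defines the subset also differs between the arms. An as-randomised comparison of 1-year QALYs, post-discharge costs and other major morbidity then lacks data by design for one group of patients in each arm.

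These patients matter to a test of policy. Without a rupture, a patient in the strategy arm is redirected after CT, while a counterpart in the control arm may first have a laparotomy. Any difference in their later recovery, readmissions or quality of life is a consequence of the two policies.

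A later analysis plan cannot repair this, because EQ-5D responses and community service use that were never requested cannot be recovered. Cost-effectiveness and other major morbidity are both named secondary outcomes.

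**Working it through.** **1. Which outcomes are affected**

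- 24-hour, 30-day, in-hospital and 1-year mortality: collected for all randomised patients. Not affected.
- In-hospital costs: Cost measurement records surgery, post-operative interventions and days in critical care and on wards for both groups, with no rupture condition. Not excluded by the follow-up sentence.
- Complications and reinterventions related to ruptured AAA repair: conditional on repair by definition. Not a conflict.
- EQ-5D at 3 months and 1 year, community service use at 1 year, and active recording of readmissions: confirmed ruptured AAA only. Affected.
- Mid-term EQ-5D: the mailing sentence speaks of surviving patients without qualification. However, it follows the restriction, and Frequency and duration of follow-up counts the questionnaire from AAA repair. Affected on the natural reading.
- Other major morbidity in 1 year: Outcome measures lists it without a rupture condition, but Planned analyses says "major morbidities after repair of ruptured aneurysm will be compared using the log-rank test and Cox regression". Affected.

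**2. Reproducing the protocol's arm mortalities**

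Inputs from Proposed sample size: 30-day mortality 47% after open repair and 21% after endovascular repair; 55% suitable; 5% without ruptured AAA.

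- Open arm: 0.95 × 0.47 = 0.4465 (protocol: 44.6%).
- Strategy arm: 0.55 × 0.21 + 0.40 × 0.47 = 0.1155 + 0.1880 = 0.3035 (protocol: 30.4%).

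Both agree. They do so only if the 5% without rupture contribute no deaths, so zero mortality in this group is the protocol's own working assumption.

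**3. Size of the group outside active follow-up**

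- Per arm: 300 × 0.05 = 15, or 30 of 600.
- Open-arm 30-day survivors: 300 × (1 − 0.446) = 166.2. Share: 15 / 166.2 = 9.0%.
- Strategy-arm 30-day survivors: 300 × (1 − 0.304) = 208.8. Share: 15 / 208.8 = 7.2%.

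The share of survivors is the relevant measure, because post-discharge data come only from survivors.

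**4. Sensitivity to the 5%**

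Planned interventions uses about 5% for patients with no AAA on CT, while Proposed sample size uses 5% for patients with no ruptured AAA. Patients with an intact AAA also fall outside confirmed rupture, so 5% may be low. At an assumed 10%, keeping the case mix among ruptures:

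- Open arm: 30 / [300 × (1 − 0.90 × 0.47)] = 30 / 173.1 = 17.3%.
- Strategy arm: 30 / [300 × (1 − 0.90 × 0.3035 / 0.95)] = 30 / 213.7 = 14.0%.

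**5. What the restriction can do to an estimate**

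If 5% are removed equally from both arms and the policies do not differ in their effect on those patients, the confirmed-only difference is 1 / 0.95 = 1.05 times the as-randomised one.

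If recognition differs by arm, a difference can arise from nothing. As an illustration, with inputs that are assumptions and not from the protocol, let 10% in each arm truly have no rupture, let the 1-year QALY be 0.40 with rupture and 0.75 without, and let there be no treatment effect. The mean in the followed subset is:

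- (0.90 × 0.40 + 0.05 × 0.75) / 0.95 = 0.418 where half of the non-ruptures are recognised;
- (0.90 × 0.40) / 0.90 = 0.400 where all are.

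The spurious difference is 0.018 QALYs. Its sign depends on which arm recognises more, and the protocol does not settle that.

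**The case against.** The strongest reply is that this is a limit on data collection, not a rule for analysis. The protocol nowhere confines the cost-effectiveness analysis to confirmed ruptures, says that missing EQ-5D and cost data will be addressed, knows survival for everyone, and describes consent to use routine records, which could supply readmissions. The group is small and is assumed equal in the two arms.

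Much of this stands, but it does not close the gap. Routine records do not hold EQ-5D or questionnaire-based community service use. Imputation is also weak here, because no patient without rupture would be actively followed in either arm. Their values would have to be borrowed from patients recovering from rupture repair, with nothing to check the assumption against. The anticipated 10% who miss the 1-year visit are a different case, since others like them are observed.

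Three stronger readings are tempting and are not supported:

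- **That the cost of laparotomy in control patients without rupture is lost.** The restriction begins after discharge, whereas surgery, anaesthesia and critical care come before it. Cost measurement covers both groups without a rupture limit, and the per-patient payment, stated per patient randomised, includes in-hospital data. The local co-ordinator is "responsible for reporting the data on all patients with ruptured aneurysm at that centre", but that is a reporting duty and does not say that other randomised patients go unreported. Diagnostic accuracy and patient disposal, both secondary outcomes, need in-hospital data on exactly these patients. Nor would every such control patient have a laparotomy: very stable patients may be imaged first, and transfers may arrive with a scan. No cost figure should be attached on this ground.
- **That exclusion is unequal and the bias has a known direction.** The two routes of confirmation make unequal exclusion possible, but the protocol assumes 5% in both groups.
- **That all morbidity comparisons are compromised.** Those tied to repair of a rupture are conditional by definition.

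**Conclusion.** The point holds in a narrow form. The protocol promises a comparison of the groups as randomised. For 1-year and mid-term QALYs, post-discharge costs and other major morbidity, it collects data only in a subset that is identified after randomisation, by different routes in the two arms. Without imputing data that were never collected, those comparisons describe confirmed ruptures and not the policy tested.

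The size is about 15 patients per arm, or 9.0% of open-arm and 7.2% of strategy-arm 30-day survivors. This rests on the protocol's 5% and on its implied zero mortality in these patients. The shares rise to 17.3% and 14.0% if the proportion is 10%. The effect on the incremental estimates cannot be signed or sized from the document. The primary outcome and all other mortality outcomes are safe. The change should be made because the data, once missed, cannot be recovered.

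**What to change.** Amend Frequency and duration of follow-up and Patient compliance and loss to follow-up so that:

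- all randomised survivors, whatever the final diagnosis, are sent the EQ-5D (3 months, 1 year, mid-term) and the 1-year service-use questionnaire, by post where no clinic visit is due;
- these contacts are timed from randomisation, because patients without a repair have no repair date;
- readmissions and other major morbidity are recorded for the same patients.

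In Planned analyses, make the as-randomised population primary for cost-effectiveness and other major morbidity, with confirmed ruptured AAA as a supportive analysis. Leave complications and reinterventions of ruptured AAA repair conditional, and say so.

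The cost is about 30 extra patients. At £50 for each of three follow-ups (Justification of support requested), that is 30 × 3 × £50 = £4,500 at most, and less after deaths. The protocol already provides for mailing the EQ-5D. Ethical issues to be addressed describes consent to quality-of-life assessment at 3 and 12 months for patients generally, and treats return of the mid-term form as implied consent.

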manuscript(s)			 	 			 															
HTA report &																						
final results			Ļ			I	 		 	I		Ļ				.	Ļ	 	L			
Legend	Set up Intense activity Low intensity completed								sity a	activ	rity											
			mpl	etec	, r				 													
	_				isive	Э		—	со	mpl	etio	n										
1		ac	tivit	v			1									1					1	1

VS 30-day mortality results presented to investigators at Vascular Society November 2013

7 Justification of support requested

Research support The support requested is for the research costs, including staffing and research costs to the participating centres. The use of the novel technology, eEVAR may be associated with cost savings because of shorter stays in critical care and hospital beds [8,36]. The collection of clinical data and monitoring of this data is onerous and will be a research cost enabled by adding time to the current EVAR trial co-ordinators, listed in references 15,16. Each participating centre will receive up to £5000 to support local research infrastructure and then £325 per patient randomized (£225 for the in-hospital data and audit and £50 each for 3m , 1y and mid-term follow-ups).

The trial manager (supervised by Professors [name], [name] & the International Centre for Circulatory Health) will be responsible for checking centre eligibility, facilitating approvals at each participating centre, chasing missing data and monitoring data and compliance with the consent process, as well as working with the local trial co-ordinator and nominated clinicians, to ensure the on-going training available for rotating staff. The role of parttime statistician (supervised by Professor [name]), who will be involved in all aspects of the trial including preparing interim reports for committees and final data analysis and part-time health economist (supervised by Dr [name]) to focus on the cost-effectiveness aspects of the trial, including final analysis and data-modeling, may be combined with the appointment of [name] (previous experience in both roles from the MRC supported MASS trial [14]). Office, publication and travel costs are necessary to support all staff and the principal investigator. Randomisation and web-based data capture will be conducted through thesealedenvelope.com. The Trial Manager will deliver training on web-based data capture and the taking of consent during the site initiation visit, which will take place once local approval has been granted. [name] and [name] will deliver aspects of organizational training for eEVAR. All CT scans (anticipate 650) will be read in a core laboratory (already established at Imperial College by [name]) at £40 per scan and patients leaving hospital alive will be flagged for date and cause of death with the NHS Information Centre. Travel costs are necessary to underpin committee and participant meetings and the for the trial manager to visit the trial centres to monitor data quality. In the final 6 months of the project secretarial help is requested to facilitate the timely delivery of manuscripts and reports.

NHS support costs

There may be very minor NHS costs accrued from a policy of diverting ambulances to the large vascular centres (where this trial will take place), but this is a policy already in effect in the large metropolitan (e.g. London, West Yorkshire) and many other areas (e.g. Dorset). The costs of obtaining patient consent have been listed as an NHS support cost.

Treatment costs The treatment costs are based on the published costs for ruptured aneurysm [36,37], the costs for acute treatment of AAA by either open or endovascular repair [8], the costs of the principal components of care taken from elective procedure [15] and the mean number of days for intensive care and hospital stay taken from UK data and Cochrane reviews, all updated to 2008-9 values [9,36]. The Cochrane review shows that the procedure time (use of operating theatre) is shorter for endovascular repair and that the time on intensive care is reduced to a mean of 2 days (versus 5.2 days for open repair) [8,23]. Similarly endovascular repair is associated with a reduced usage of blood products and length of ward stay. Treatment costs have been estimated for 200 patients undergoing endovascular repair versus 400 undergoing open repair (300 randomised to open repair and 100 not anatomically suitable for eEVAR). Endovascular repair has higher procedure costs, which includes the endografts and higher reintervention costs. On average open repair is a associated with increased time in the operating theatre, increased administration of blood products, increased usage of critical care and vascular surgery ward beds, so that overall this may be the more expensive option, in concordance with published data [8,36]. In the Netherlands the hospital costs of endovascular repair have been estimated recently at 17000€ versus 21000€ for open repair [36]. These values are similar to our listed costs of £15,000 for endovascular repair and £15,700 for open repair, which includes the follow up to 1 year.

However, the is trial is likely to place an added burden on intensive care facilities in the participating hospitals, much of this as a result of the 1:1 randomisation (which increases the number of patients undergoing open repair). Additional central support for Critical care usage, in excess of £500,000, may be necessary.

8 References

1 Bown MJ et al A meta-analysis of 50 years of ruptured abdominal aortic aneurysm repair Br J Surg 2002;89:714-730

2 Best VA et al Meta-analysis and systematic review of the relationship between volume and outcome in abdominal aortic aneurysm surgery. Br J Surg 2003;90:1510-5

3 Norman P, [name] JT Abdominal aortic aneurysm: the prognosis in women is worse than men.Circulation 2007;115:2865-9

